76. Centers for Disease Control. Cancer Registry Research Approval Process: Classification of States by Level of Approval Required2018.

ANALYSES

Quantitative Data:

- Differences in cancer survivorship performance indicators before and after intervention were assessed using Chi-square or Fisher Exact tests.
- Clinical characteristics are summarized with frequencies and percentages.
- Demographic and patient characteristics are summarized descriptively with respect to frequencies and percentages for categorical variables, and mean, standard deviation, median, minimum and maximum for continuous variables.
- Differences in surveillance rates by tumor types before and after intervention were assessed using Fisher Exact tests.
- Statistical tests were considered significant if $p < 0.05$.

Qualitative Data:

- Interview notes, transcripts of practice facilitation meetings, and field records were compiled and analyzed using the i-PARIHS framework to evaluate barriers and facilitators to implementation.
- A thematic network analysis was employed by first noting initial impressions.
- Transcripts were independently reviewed line-by-line and preliminary codes were applied to relevant passages.
- A coding framework was developed with clear code descriptions, organizing data into themes and sub-themes.
- This framework was systematically applied to all transcripts using Dedoose software to ensure consistent and meaningful codes across the dataset.

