
Specific Aim 2. Evaluate the effectiveness of KanSurvive-ECHO for enhancing evidence-based survivorship care for rural breast, colorectal, lung, and prostate cancer survivors. Hypothesis: Compared to delayed intervention control, rural primary care practices randomized to KanSurvive-ECHO will demonstrate greater concordance with evidence-based survivorship care guidelines as measured by a composition score determined by change in EHR documentation consistent with guideline concordant care.

Specific Aim 3: Utilizing the Integrated Promoting Action on Research Implementation in Health Services (i-PARIHS) framework (6) describe key facilitators and barriers to implementation of KanSurvive-ECHO including innovation, recipients, context, and facilitation. This novel project will provide a model for development of a community of practice using practice facilitation and Project ECHO to improve the management and follow-up of cancer survivors in the acute and extended phases of cancer survivorship.

B. Background and Significance

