Practice facilitation. Through more intensive practice facilitation onsite and through ECHO activities, we aim to improve care delivery by creating an ongoing, trusting relationship between all practice staff and an expert facilitator who will help clinic staff redesign workflows and improve quality.(18) This promotes a clinical culture of learning, consensus building, goal setting, quality improvement, and achievement, as demonstrated by the Institute for Healthcare Improvement's Learning Collaborative Breakthrough Series,(19) (20). One study using similar methods, the EPIC cluster randomized trial, used a practice facilitation intervention to produce a 100% increase in diabetic patient foot examinations, compared to a 33% increase in a control arm, which used self-directed provider education for quality improvement.(21) Rural clinics in this study will use brief plan-do-study-act cycles, to improve clinic and provider adherence to cancer survivorship care guidelines. The steps involved include: 1) practice-level discussion until reaching consensus on a specific, measurable, quality-improvement goals for using electronic health records (EHRs) to improve survivorship care clinical performance; 2) identifying barriers to implementation in achieving the goal; 3) selecting one or more changes to improve the status quo in survivorship care; 4) instituting these changes; and 5) measuring change in provider and clinic performance via assessments of EHR change for cancer survivors in the practice. In successive cycles, practice staff will brainstorm ways to overcome emerging barriers to achieving plan-do-study-act goals. We will support this process using visiting practice facilitators assigned to rural primary care practices. Facilitators will be trained and certified using the University of Buffalo Practice Facilitator online training program (22) and will be selected and assigned based on previous experience working with rural teams. Practice facilitators will in turn train practice staff to use a consistent approach for quality improvement work and workflow redesign. Facilitators will communicate at least weekly with a clinic-designated nurse or practice manager in each rural study practice (the Practice Champion), and at least monthly with a clinic physician designated as the Practice Lead. The role of the Practice Champion and Lead will be to legitimize the intervention in their clinics, assist with training/orientation of other clinicians and clinic staff, and ensure response to facilitators and EHR data being fed back to practices. The Facilitator will aim to maximize inter-professional impact by coaching Practice Champions and Leads to use a team-building, collaborative approach adapted to the organizational context of each practice. Facilitators will

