
Approach: Research Design will include observational research plus pilot testing of the KanSurvive-ECHO intervention

Conceptual Framework: Informed by the Integrated Promoting Action on Research Implementation in Health Services (i-PARIHS) implementation framework, the KanSurvive intervention will target EBP improvement in rural primary care. Our recent pilot work using an updated 4-session case-based curriculum relied on utilization of practice facilitators providing on-site training to rural primary care teams. This project will expand to move beyond traditional training models, to a hands-on practice re-organization. Additional formative data collection with site visits and practice observation will inform final refinement of the KanSurvive ECHO Intervention. The delayed intervention control and KanSurvive-ECHO practices will be compared on outcomes specified by the RE-AIM evaluation framework (e.g., Reach, Effectiveness, Adoption, Implementation fidelity and acceptability, and Maintenance after 6 months).

Study Design: Using a Hybrid Type II study design, (51) the proposed study includes a three-aim plan for further assessing the rural practice environment and refining the KanSurvive-ECHO intervention (Aim 1), testing the effectiveness of KanSurvive-ECHO (Aim 2), and describing key facilitators and barriers to adoption of KanSurvive-ECHO intervention components in rural primary care (Aim 3). We will recruit 20 rural (defined using RUCA-UR codes) primary care practices from the KPEPPER network for a delayed intervention control trial.

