Intervention refinement: The research team will work to review Phase 1 data with participating practice leads and champions, Rural ACO leaders and transformation specialists, regional content experts, and the KPPEPR Board to come up with a set of 4-8 major recommendations for intervention. They will then review previously developed pilot KanSurvive materials and suggest refinements based on these major recommendations. The research team and staff will utilize these suggestions to refine and finalize the KanSurvive intervention for Phase 2 (See Figure 6, Suggested study schema).

4.6 Phase 2: Implementation of the cluster-randomized controlled trial, with delayed start control arm Figure 6: Suggested Study Schema

Practice Facilitation. Due to the complexity of translating evidence-based guidelines into practice, significant gaps continue to exist between research evidence and practice.(58, 59) Knowledge is rarely sufficient to support the adoption of EBP behavior,(60, 61) with didactic education or passive dissemination strategies largely ineffective. Practice facilitation has emerged as an effective practice change approach and will be a key implementation strategy in the proposed study. Taken literally, facilitation means “to make easier”. (56, 62)Practice facilitation is broadly defined as “a supportive service provided to a primary care practice by a trained individual or team of individuals. (63)These individuals use a range of organizational development, project management, quality improvement (QI), and practice improvement approaches and methods to build the internal capacity of a practice to help it engage in improvement activities over time and support it in reaching incremental and transformative improvement goals. This support may be provided onsite, virtually (through phone conferences and Webinars), or through a combination of onsite and virtual visits” (AHRQ, <https://pcmh.ahrq.gov/page/practice-facilitation>). Practice facilitators, also known as practice coaches or quality improvement coaches, are specially trained individuals who help practices engage in implementing guidelines and developing capacity for continuous quality improvement. (18)

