2. *Effectiveness* will be measured as % change in electronic health record evidence of guideline concordant care from pre- to 6-months post- KansSurvive-ECHO in intervention versus delayed intervention control practices. Using baseline EHR assessments in charts of cancer survivors identified from hospital registries we will compare the pre- and post- percentages of these survivors with best practice alerts, orders sets, health maintenance modules or other tools that note specific survivorship care services that they should be receiving to meet guidelines (Table 3) (67-74)

3. *Adoption* will be measured by calculating the representativeness of the participating rural primary care practices. Specifically, participating rural primary care practices will be measured on their size and their patient panels and will be compared as a group to the overall data that is available for all rural primary care practices in the state of Kansas on these key variables to assess for the representativeness of participating practices.

4. *Implementation Consistency: In addition to project feasibility and acceptability, we will assess facilitators and barriers to KansSurvive adoption using the i-PARIHS framework (Aim 3). Fidelity:* We will refine KansSurvive fidelity assessment consistent with Schoenwald et al.(55): (1) identifying relevant components for monitoring across practice facilitation and ECHO components (e.g., specificity, necessity, degree of precision), (2) determining who would provide the ratings, (3) obtaining the ratings, and (4) creating a summary score for the ratings. We will monitor fidelity to the KansSurvive components, with checklists associated with practice facilitation from multiple perspectives (e.g., participating practice teams, facilitators, ECHO subject matter experts). *Attendance and Participation.* Percent attendance will be

calculated for each rural primary care practice as the percent of practice facilitation and ECHO sessions attended divided by the total number of sessions offered. For both groups' participation the amount of between session work completed (as a percent).

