Diet/exercise/smoking cessation (annual)						
Review of Family History of Cancer (one time)	X	X	X	X		
Evidence of Changes to "Problem List" (one time, cancer diagnosis or history of)	X	X	X	X		
Evidence of Changes to "Health Maintenance/Preventive Services" or "Order/Smart set" or "Smart Phrases" or "Annual Wellness Visits" Since Cancer Diagnosis (one time)	X	X	X	X		
Treated with Anthracycline Y or N**						
ECHO Cardiogram (frequency specified by risk) **						
Bone Mineral Density (treated with anti-hormone or androgen deprivation therapy) (frequency specified by risk) **						

*if not deemed medically necessary, is their clarification in EHR (e.g., due to type of cancer surgery - total colectomy or bilateral mastectomy)

** exploratory variables: applicable to subset of patients based on treatment exposure

Limitations and strengths to EHR data are inherent to this type of project. There will be cancer survivors missed by the method of using local hospital registries, however, >95% of referrals from our focus group primary care providers are to the same oncologist/practices (49), thus keeping missing cancer survivors to a minimum. Use of a trained honest broker for data extraction will reduce the confounder of a lack of familiarity with EHR and where to find documentation within the EHR also will eliminate potential bias within the practice and patient population.

Study Timeline

Phase/Activity	Year 1	Year 2	Year 3	Year 4	Year 5
----------------	--------	--------	--------	--------	--------

4.9 Dissemination and Future Plans:

Using the i-PARIHS and RE-AIM frameworks for evaluation, relevant findings will be submitted for abstract (poster or presentation) at regional and national meetings and to peer-reviewed

Patient & advisory board engagement	x	x	x	x	x	x	x	x	x	x
Phase 1	x	x	x							
Site recruitment	x	x								
Workflow analysis		x	x							
Assess practice & EHR capabilities + P30 rural supp		x	x							
Explore facilitators & barriers of successful process		x	x					x	x	
Finalize intervention & assessment tools			x	x						
Phase 2				x	x	x	x	x	x	x
Intervention				x	x	x	x			
Wave 1				x	x	x				
Wave 2						x	x	x		
Data extraction							x	x		
Evaluation							x	x		
Data analysis, Dissemination								x	x	
Identify opportunities-sustain community of practice								x	x	

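### The only tests specified are before/after comparisons, so nothing tests the randomised comparison with delayed control that Aim 2 promises

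*Combined protocol and SAP*

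**What the plan says.** Four places in the protocol commit to a comparison between randomised arms.

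- Specific Aim 2, hypothesis: "Compared to delayed intervention control, rural primary care practices randomized to KanSurvive-ECHO will demonstrate greater concordance with evidence-based survivorship care guidelines". The outcome named for this is a composite score based on how the health-record entries change.
- Approach, Conceptual Framework: "The delayed intervention control and KanSurvive-ECHO practices will be compared on outcomes specified by the RE-AIM evaluation framework".
- Section 4.6, Phase 2 heading: "Implementation of the cluster-randomized controlled trial, with delayed start control arm".
- Evaluation: RE-AIM, item 2 (Effectiveness): the measure is the percentage "change in electronic health record evidence of guideline concordant care from pre- to 6-months post- KansSurvive-ECHO in intervention versus delayed intervention control practices".

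The ANALYSES section at the end of the document is the only place in the text available for review that names statistical tests. Under Quantitative Data it has two inferential lines. The first reads "Differences in cancer survivorship performance indicators before and after intervention were assessed using Chi-square or Fisher Exact tests". The second applies Fisher exact tests to surveillance rates by tumour type, also before versus after. The remaining quantitative bullets are descriptive summaries and the 0.05 significance threshold.

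**The concern.** Neither test refers to arm, control, randomisation, the composite score or the practice. The section also leaves open whether the before/after contrast uses intervention practices only or all 20 pooled. On either reading it estimates change over time, and improvement that would have happened anyway is counted with any effect of KanSurvive-ECHO.

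Upward change without an intervention is likely for part of this outcome. Table 3 has six non-exploratory items. Three of them are recorded once only: family history review, the problem-list change, and the health-maintenance or order-set change. In a fixed group of survivors such entries can accumulate but should not disappear.

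The protocol's own background shows that a control arm can improve. In the diabetes facilitation trial cited under Practice facilitation, a 100% increase in foot examinations is "compared to a 33% increase in a control arm, which used self-directed provider education for quality improvement". That control arm received an educational intervention, so the 33% does not estimate background drift here.

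At stake is the trial's main claim. A small before/after p-value could be reported as effectiveness when both arms moved equally, and the analysis would make no use of the randomised control.

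**Working it through.** **1. Commitment against analysis**

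| Element | Protocol body | ANALYSES section |
|---|---|---|
| Contrast | Intervention v. delayed control | Before v. after |
| Outcome | Composite concordance score | Separate indicators; surveillance rates by tumour type |
| Randomised unit | Practice (20) | Not mentioned |
| Test of the arm contrast | None named | None named |

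The documents give no power, effect size, ICC or allocation ratio, so there is no planned figure to reproduce. The rest is illustration under stated assumptions.

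**2. Inputs**

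- From the documents: 20 practices; an average of 200 survivors per clinic (Recruitment of sites); significance level 0.05.
- Assumed: two-sided tests, 10 practices per arm, baseline 50% or 60%, zero intervention effect, and a drift common to both arms.
- The number of charts to be analysed is not stated, so a range is used. If all 200 survivors per clinic were used, one arm would give 10 × 200 = 2,000 records per period and all practices 20 × 200 = 4,000.

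**3. Before/after test, independent records**

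The smallest significant difference at a 50% baseline is 1.96 × √(2 × 0.25 / n).

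For a drift d from p0 = 0.60 to p1, the rejection probability is approximately Φ((d − 1.96·s0)/s1), plus a negligible or small opposite tail. Here s0 = √(2·p̄(1 − p̄)/n), p̄ is the mean of p0 and p1, and s1 = √([p0(1 − p0) + p1(1 − p1)]/n).

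Worked case, n = 2,000 and d = 0.05:

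- p̄ = 0.625
- s0 = √(2 × 0.234375/2,000) = 0.01531
- s1 = √((0.24 + 0.2275)/2,000) = 0.01529
- (0.05 − 0.03001)/0.01529 = 1.308, giving 90.5%

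| Records per period | Smallest significant drift (50% baseline) | 5-point drift from 60% | 2-point drift from 60% |
|---|---|---|---|
| 200 | 9.8 points | 18% | 7% |
| 500 | 6.2 points | 37% | 10% |
| 2,000 | 3.1 points | 90.5% | 25% |
| 4,000 | 2.2 points | 99.6% | 45% |

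**4. Before/after test against a between-arm comparison**

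Simulation with 4,000 runs: 10 practices per arm, practice rates beta-distributed with mean 0.60 and ICC 0.05, and a 5-point drift in both arms. The between-arm test regresses the practice's follow-up rate on arm and baseline rate (t, 17 df).

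| Records per practice | Before/after, intervention practices | Before/after, all practices | Between arms |
|---|---|---|---|
| 20 | 18% | 30% | 4.5% |
| 50 | 36% | 64% | 5.3% |
| 200 | 91% | 99.5% | 5.1% |

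If the drift also varies between practices (SD 3 points), the between-arm test rejects 5.5%, 5.6% and 4.3% of the time.

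**5. Ignoring practice, with no drift**

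A second simulation let each practice's rate vary between periods, with 80% of the between-practice variance persistent and 200 survivors per practice. With no drift and no effect, the all-practice before/after test rejects 5.4%, 9.6%, 25.3% and 38.5% of the time at ICC 0, 0.01, 0.05 and 0.10. A t test of practice-level change by arm rejects 4.4% to 5.6% of the time across these ICCs and shared drifts of 0, 3 and 5 points.

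**The case against.** The strongest reply is that the contrast is already in the plan: the Effectiveness item states it, and that item also says pre and post percentages will be compared, so the before/after tests carry out one planned step. This is fair. The tests are incomplete and not foreign to the protocol. But no test or model is attached to the arm contrast, and finding significance in one arm and not the other would not test the difference between them.

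The illustration can also be criticised. The Effectiveness item and Table 3 suggest that the same charts are read twice, whereas step 3 assumes independent records. With an assumed within-patient correlation of 0.5, s1² loses the term 2 × 0.5 × √(p0(1 − p0)p1(1 − p1))/n. Rejection for a 5-point drift becomes 9.5%, 32%, 97% and 100% (rounded) at 200, 500, 2,000 and 4,000 records; for a 2-point drift it becomes 1.5%, 3%, 17% and 43%. The small-sample figures in step 3 would then be too high, while the large-sample figures for the 5-point drift would not. The simulation in step 4 also holds practice rates fixed apart from the drift, so it says little about clustering; step 5 addresses that.

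The Approach calls the work pilot testing, but the same section promises to test effectiveness and Aim 2 states a comparative hypothesis. Allocation is not destroyed by an omitted test: the arm comparison can still be made if the data are kept by arm and date. None of this supplies the missing test.

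**Conclusion.** The concern holds, and the plan must be changed. Following the analysis section as written tests change over time and leaves Aim 2 untested. This rests on reading the sections side by side and depends on none of the assumed numbers. It covers the text available for review, from which some pages had been removed.

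The size of the problem depends on drift and chart count. Under the independence assumptions, a false signal is nearly certain for a 5-point shared drift with thousands of records, and much less likely for a 2-point drift with a few hundred. The baseline, drift, ICC, 1:1 allocation and chart counts are all assumptions.

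**What to change.** Reconcile the ANALYSES section with Specific Aim 2, the Conceptual Framework, section 4.6 and the Effectiveness item.

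- **Primary analysis.** Compare the follow-up composite score between randomised arms, adjusted for the practice's baseline score, with a 95% CI. Use the practice as the unit of analysis, or a model with a practice random effect and a small-sample correction for 20 clusters. A mixed model with an arm-by-time term is an acceptable alternative.
- **Composite.** Define it, since Aim 2 names it without a scoring rule. One example is the share of the six non-exploratory Table 3 items, where applicable, met per survivor and averaged within practice. State how an item recorded as not medically necessary is scored.
- **Data cut.** Use only follow-up documentation dated before control practices start the intervention. As read from the PDF, the Study Timeline's half-year columns put Wave 1 in 4 to 6, Wave 2 in 6 to 8 and data extraction in 7 to 8. The columns may be misaligned, and treating Wave 2 as the control arm is an inference. If that reading is right, follow-up 6 months after the intervention could fall after crossover, so the dates should be stated.
- **Before/after changes.** Report them descriptively.
- **If the analysis is done.** The section is written in the past tense. If results exist, re-analyse by arm and label that post hoc, or describe the results as an uncontrolled before/after comparison without an effectiveness claim.

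The cost is a scoring rule, a dated data cut and one between-arm model. No new data source is needed, provided control practices have documentation for the matching period.

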5. **Maintenance:** Our experienced team will conduct structured interviews with participating rural primary care practices to assess their ability to sustain key components of the KanSurvive ECHO program over time and maintain effects at 6-months, including policies and procedures to support the cancer survivorship guidelines. Identification of cancer survivors with breast, lung, colon and prostate cancer. In order to identify survivors under the care of a particular PCP, we will engage the local/affiliated hospital's tumor registry. A list of all primary care providers participating in the intervention will be compiled using several key fields: "following doctor" (primary care provider) and the type of cancer (breast, colon, lung, and prostate cancer). This PCP list will be given to local hospitals, which will run a report to identify all cancer survivors with breast, lung, colon and prostate cancer affiliated with the "following doctor". Additional variables from the tumor registry will include demographics, stage, treatment, treating oncologist. Each primary care provider participating in the intervention will receive their list of affiliated patients. (75)

Data extraction will be completed by an "honest broker" who will utilize a consistent algorithm across all EMR systems to record evidence of guideline concordant survivorship care through a HIPAA waiver to allow such data abstraction without consenting individual patients. Medical record extraction is considered the "gold standard" and will be the primary objective data source for this trial. Practice-level data gathered from participating practices will be recorded directly into a secure KUMC REDCap database which requires username and password verification. Only designated research staff will have access to research information. The data collection survey tool built in REDCap will be pilot tested internally and modified as needed to ensure clarity for the data collector.

Table 3: Measure change in EHR documentation Concordant with Evidence-based Cancer Screening by Diagnosis

Cancer Diagnosis	Breast	Lung	Colon	Prostate	EHR Documentation Baseline (Yes/No)	EHR Documentation Post (Yes/No)
Recommended screening based on diagnosis*	Mammogram (annual)	CT (annual)	Colonoscopy (frequency specified by risk)	PSA (annual or more frequent based on risk and time since diagnosis)		
Distress/Depression Screen (PHQ9) (annual)	X	X	X	X		
Lifestyle Recommendations	X	X	X	X		

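### The unpaired before-after chi-square and Fisher tests ignore both repeat reading of survivors and practice-by-period variation, so the true error rate behind p<0.05 is unknown in size and direction

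*Combined protocol and SAP*

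**What the plan says.** Under ANALYSES, Quantitative Data, two inferential procedures are listed. The first reads "Differences in cancer survivorship performance indicators before and after intervention were assessed using Chi-square or Fisher Exact tests". The second reads "Differences in surveillance rates by tumor types before and after intervention were assessed using Fisher Exact tests". The threshold follows: "Statistical tests were considered significant if" p<0.05. Sidedness is not stated.

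The design text describes data with two levels of dependence.

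- **Practices.** The heading of section 4.6 is "Implementation of the cluster-randomized controlled trial, with delayed start control arm", and the Aim 2 hypothesis is that "rural primary care practices randomized to KanSurvive-ECHO will demonstrate greater concordance with evidence-based survivorship care guidelines". Survivors are therefore grouped within about 20 practices.
- **Repeat readings.** The Effectiveness item under Evaluation: RE-AIM says "we will compare the pre- and post- percentages of these survivors", and Table 3 places a baseline yes/no column beside one labelled "EHR Documentation Post (Yes/No". On a plain reading, the same charts are read twice.

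Table 3 also marks three items as needing documentation only once. One is "Review of Family History of Cancer (one time"; the others are the problem-list entry and the health-maintenance or order-set entry.

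In the text available, no paired test, mixed model, GEE, practice-level analysis, ICC or design effect is named. Recruitment of sites gives 200 as the average number of survivors a practice cares for, but the number of charts abstracted per practice is not given.

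**The concern.** A chi-square or Fisher test on a before-after two-by-two table assumes that all readings, within and across periods, are independent. Two features break this, in opposite directions.

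1. If the same survivor is read twice, the two readings are positively correlated. The before-after difference then varies less than the test assumes, and the test is conservative.
2. If practices drift differently between the two periods, readings within a practice and period move together beyond what the practice's stable level explains. The difference then varies more than the test assumes, and the test is liberal.

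Stable differences between practices largely drop out of a before-after contrast. Randomising practices is therefore not itself the cause; practice-by-period variation is.

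These are the only inferential tests in the available text, so any significance claim rests on them. A reader cannot tell whether a reported p<0.05 was too easy or too hard to reach.

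**Working it through.** **Plan's own figure.** The only error-rate figure is p<0.05. With independent readings, a two-sided test at 1.96 gives 2Φ(−1.96) = 5.0%. There is no power or sample-size calculation to reproduce.

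**Inputs from the documents.** 20 practices; an average of 200 survivors cared for per practice.

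**Assumed inputs (none is in the documents).** Charts abstracted per practice m = 20, 50 or 200; ICC = 0.01, 0.05 or 0.10; cluster autocorrelation CAC (between-period ICC divided by within-period ICC) = 0.5, 0.8 or 1; correlation r = 0.5 between a survivor's two readings within a practice.

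**Formula.** Let τ = ICC·CAC + (1−ICC)·r. The true variance of the before-after difference, divided by the variance the unpaired test assumes, is

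V = 1 − τ + (m−1)·ICC·(1−CAC),

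and the true type I error is 2Φ(−1.96/√V).

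**Middle case** (ICC 0.05, CAC 0.8). τ = 0.04 + 0.475 = 0.515, so V = 0.485 + (m−1)·0.01. For m = 20 / 50 / 200, V = 0.675 / 0.975 / 2.475 and the error rate is 1.7% / 4.7% / 21.3%. The two effects cancel at m = 1 + 0.515/0.01 = 52.5 charts.

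**Full grid, true type I error (%):**

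| ICC | CAC | m=20 | m=50 | m=200 |
|---|---|---|---|---|
| 0.01 | 0.5 | 1.1 | 2.3 | 10.9 |
| 0.01 | 0.8 | 0.7 | 1.1 | 3.8 |
| 0.01 | 1 | 0.53 | 0.53 | 0.53 |
| 0.05 | 0.5 | 4.7 | 13.6 | 40.2 |
| 0.05 | 0.8 | 1.7 | 4.7 | 21.3 |
| 0.05 | 1 | 0.45 | 0.45 | 0.45 |
| 0.10 | 0.5 | 10.4 | 25.4 | 54.4 |
| 0.10 | 0.8 | 3.4 | 10.4 | 35.3 |
| 0.10 | 1 | 0.35 | 0.35 | 0.35 |

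The range is 0.35% to 54%. Nine of 27 cells exceed 5%: one at 20 charts, three at 50 and five at 200. All nine cells with CAC 1 are conservative. Simulation with 20 practices (4,000 runs per cell) gave 0.3% to 55% for the unpaired chi-square, against 4.3% to 5.7% for a paired t test on practice changes.

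**If different survivors were read at the two times** (r = 0), the same grid runs from 3.9% to 55%, with 18 of 27 cells above 5%.

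**Pairing alone.** McNemar's test removes τ but still ignores practice. Its variance ratio in the middle case at m = 200 is 2.475/0.485 = 5.10, giving 2Φ(−1.96/√5.10), about 38%.

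**Tumour-type subsets.** Simulated with ICC 0.05, CAC 0.8, r 0.5 and a rise from 60% to 70%, Fisher power at 5 / 10 / 20 / 50 charts of a type per practice is 21 / 53 / 87 / 99.7%. A paired t on 20 practice changes gives 51 / 76 / 93 / 99.6%. The near-equality at 50 charts reflects both tests reaching their ceiling. With CAC 1, 50 charts and 60% to 65%, V = 0.475 and the unpaired z is 0.05/√(0.4675/1000) = 2.31. Unpaired power is Φ((2.31−1.96)/√0.475), about 70%. Paired t (noncentral t, 19 df) gives about 89%.

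**One-time items.** A recorded yes on these would normally stay yes (an inference), so readings can mostly only rise. The symmetric grid does not describe them.

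**The case against.** The strongest reply is that the direction is unknown, most of the grid (18 of 27 cells) is at or below 5%, and every ICC, autocorrelation and correlation is assumed. Aim 2 is also a between-arm hypothesis, so the before-after tests might be regarded as secondary. All of this is fair, and it rules out a claim that the tests are anti-conservative. It does not rescue the stated threshold: the dependence follows from the design text, and only its net effect depends on the assumed values.

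Three stronger readings are tempting and are not supported.

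- A reader might apply the usual design effect, 1+(m−1)·ICC, and conclude that false positives are inflated because practices were randomised. That factor belongs to a comparison of different practices; stable practice differences largely cancel here.
- A reader might conclude that lost power in the tumour-type tests disappears at about 50 charts per type. That holds only in the particular case simulated; the 70% versus 89% example shows a loss persisting.
- A reader might assume that all 20 practices supply a usable change. The Effectiveness item sets intervention against delayed-control practices, and the Study Timeline has two waves. If both arms were read at the first wave's follow-up, 20 changes would mix treated with untreated practices.

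It also stands that the unit of analysis and the linkage of charts are inferred from the yes/no items and the tests named, not written out.

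**Conclusion.** The point holds in limited form. The listed tests assume independence that the design does not provide, and the plan gives none of the quantities needed to say what p<0.05 means. Under the assumed ranges the true error rate lies anywhere from 0.35% to 54%, on either side of 5%. It rises with the number of charts per practice whenever practices drift differently over time.

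This rests on the same survivors being read twice, on patient-level readings being the unit, and on the assumed r, ICC and CAC. If different survivors were read, the tests lean towards the liberal side. The range does not apply to the one-time items; for these, an uncontrolled before-after p-value partly reflects elapsed time, whatever test is used.

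The absence of a between-arm test is a separate matter and is not counted here.

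**What to change.** 1. Replace the chi-square and Fisher tests, including those by tumour type, with a paired t or permutation test on practice-level changes (post rate minus baseline rate).
2. Use only practices whose baseline and post readings bracket their own intervention period. That is 20 practices if each wave was read around its own start, and otherwise the intervention arm only (10 if allocation is 1:1, which the documents do not state). Do not pool untreated control-period changes with treated ones. With 10 practices, paired-t power in the tumour-type case above (60% to 70%, CAC 0.8) falls to about 26 / 42 / 63% at 5 / 10 / 20 charts.
3. Report one-time items descriptively, or only as a change compared with control practices.
4. Alternatively, report all before-after changes without a significance claim.
5. If linked patient readings exist, a mixed model with practice, practice-by-period and patient effects and a small-sample correction is an option. McNemar's test alone is not enough.
6. Report the charts abstracted per practice and the ICC.

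The cost is low: standard software and per-practice rates suffice for items 1 to 3, with no patient linkage. The section is written in the past tense, so some re-analysis may be needed, and p-values may rise.
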